## 6. Patient Disposition

The number of patients who were screened will be displayed. The number and percentage of patients who randomized, initiated, completed, or discontinuing treatment will be displayed using the following categories for all-randomized population and all-randomized population – Extension Study Period subset by treatment group and part.

- Screened
  - Screening Failure
- Randomized
- Initiated first course of treatment in Main Study Period
  - Complete first Course in Main Study Period
  - Discontinued during first Course in Main Study Period
- Initiated second course of treatment in Main Study Period
  - Complete second Course in Main Study Period
  - Discontinued during second Course in Main Study Period
- Initiated treatment in Extension Study Period
  - Complete Extension Study Period
  - Discontinued Extension Study Period

The reasons for screening failure will be displayed using the following categories and ordering:

- Inclusion/Exclusion Criteria Not Met
- Patient Withdrew Consent
- Others

The screening failure summary will include the number of patients out of all screened patients and the primary reason for screening failure. A listing of patients reported as screening failures will also be provided.

The reasons for discontinuation will be displayed using the following categories and ordering:

- Patient develops sign of disease progression
- Patient experiences no efficacy from study drug
- Patient withdraws consent or patient refuses
- Patient develops any malignancy
- Adverse Event
- Significant or major protocol violation
- Lost to follow-up

- Patient died
- Investigator decision
- Sponsor terminates the study
- Pregnancy
- Other

In addition, the treatment duration in days (calculated as date of last visit - date of first infusion in study period + 1) will be calculated and be summarized for patients who discontinue study treatment prematurely. The date of first infusion will be taken as the earliest date recorded on the “Study Treatment Infusion” eCRF page and the date of last visit will be taken as recorded on the “Study Termination” eCRF page.

The disposition listing will list all data collected on the “Study Termination” eCRF along with the date of first infusion for the all-randomized population.

## **7. Demographics, Baseline Characteristics, and Background Characteristics**

### **7.1. Demographics**

The following demographic measures will be tabulated for the all-randomized population and all-randomized population – Extension Study Period subset by treatment group and part: age (years); gender (male, female); female fertility status (Pre-menarche, sterile, post-menopausal, potentially able to bear children); race (white, black, Asian, other, not allowed by investigator country regulations); height (cm) and weight (kg) as recorded at the screening visit; Body-Mass Index (BMI) ( $\text{kg}/\text{m}^2$ ); country; region (EU, non-EU).

Age will be automatically calculated in the eCRF system based on the date of the informed consent visit and the date of birth provided. Patients from some countries may have the information of the year of birth only. When date and month are missing for date of birth, age will be derived using the year of birth and the year of informed consent only.

### **7.2. Baseline Characteristics**

The baseline characteristics will be also tabulated for the all-randomized population and all-randomized population – Extension Study Period subset by treatment group and part: prior anti-TNF- $\alpha$  blocker status (inadequate response vs. intolerant case); RF or anti-CCP status (both positive vs. both negative vs. either RF or anti-CCP negative); number of patients whose swollen joints (of 66 assessed) and tender joints (of 68 assessed) equal to or higher than 8 at baseline visit; duration of prior TNF-antagonist use, number of prior TNF-antagonist use, baseline CRP/ESR.

Demographic and baseline characteristic data will be listed for the all-randomized population.

### **7.3. Other Baseline Characteristics**

At screening, the following assessments will be performed:

- Hepatitis B Surface Antibody (HBsAb)
- Hepatitis B Surface Antigen (HBsAg)
- Hepatitis B Core (total) Immunoglobulin (HBcIg)
- Hepatitis B virus DNA (if HBsAg is negative, HBsAb is negative or positive, and HBcIg is positive)

- Hepatitis C Antibody
- Human Immunodeficiency Virus (HIV) 1&2

To obtain confirmation result, the following assessments can be performed:

- Hepatitis B Surface Antigen (HBsAg) (Confirmation)
- Hepatitis C Antibody (Confirmation)
- Human Immunodeficiency Virus (HIV) 1&2 (Confirmation)

A listing will be produced by the treatment group for the all-randomized population.

#### **7.4. Medical History**

Medical history is captured at the screening visit and will be coded using Medical Dictionary for Regulatory Activities (MedDRA) version 18.1 or higher. Medical history will be summarized by treatment group, study part, system organ class (SOC), and preferred term (PT). Percentages will be calculated using the number of patients in the all-randomized population and all-randomized population – Extension Study Period subset as the denominator by treatment group and part. Medical history will also be listed for the all-randomized population.

#### **7.5. Rheumatoid Arthritis History**

Rheumatoid arthritis history is captured at the screening visit and is based on the Rheumatoid Arthritis Classification Criteria 1987 [2]. The number and percentage of patients with each type of criterion will be summarized for the all-randomized population and all-randomized population – Extension Study Period subset by treatment group and part. And the descriptive statistics of time since Rheumatoid Arthritis diagnosis will be tabulated for the all-randomized population and all-randomized population – Extension Study Period subset by treatment group and part. Time (years) since RA diagnosis will be calculated as  $((\text{date of randomization (Day 0 of Main Study Period)} - \text{date of diagnosis})/365.25)$ . If an incomplete rheumatoid arthritis diagnosis date is recorded for a patient this will be imputed using the latest possible date. That is, if the day is missing (i.e. XXMAR2016) the date will be the last day of the month (i.e. 31MAR2016). If the day and month are missing (i.e. XXXXX2016) the date will be set to the 31th December (i.e. 31DEC2016). If the imputed date is later than randomization date, then it will be imputed using the randomized date. If the whole date is missing, the date will not be imputed and time since RA diagnosis will not be calculated. Rheumatoid arthritis history will also be listed by treatment group for the all-randomized population.

#### **7.6. Inclusion and Exclusion Criteria**

Details of the inclusion and exclusion criteria can be found in [Sections 4.1.1](#) and [4.1.2](#) of the protocol. Inclusion and exclusion criteria for each patient will be presented in two separate listings for all-randomized population.

A number of the inclusion and exclusion criteria may be modified during protocol revisions. The listing will indicate which protocol the patient was recruited under and hence which criteria apply. In addition, if some criteria get added during the revisions, the criteria will be renumbered for patients recruited prior to these protocol amendments in such a manner that the criteria are mapped to the numbering as per final study protocol.

## 8. Biomarkers

For patients who sign a separate informed consent form for the biomarker assessments, blood sample (central laboratory) for FcγR genotype (FcγRIIa, IIIa and/or any necessary genotypes), test results will be collected after randomization and before study treatment administration on Day 0 of Week 0.

Data for each genotype will be summarized by treatment group and part for the all-randomized population, efficacy population, all-randomized population – Extension Study Period subset and efficacy population – Extension Study Period subset. A listing will be also generated for the all-randomized population.

## 9. Treatments and Medications

All medications except co-administration of methotrexate and folic acid will be coded according to the World Health Organization drug dictionary (WHODD September 1, 2015 or later).

### 9.1. Prior and Concomitant Medications

Medications will be classed as either prior or concomitant. For the purpose of inclusion in prior and/or concomitant medication tables, incomplete medication start and stop dates will be imputed as follows:

- Missing day: Assume the day is 1st of the month.  
However, if the partial date and the date of first infusion (defined as the earliest date recorded on the “Study Treatment Infusion” eCRF page) lie within the same month and year and the date of first infusion is not after the stop date of the medication, set to the date of first infusion. Otherwise, if date of first infusion is after the stop date for the medication, set to stop date of the medication.
- Missing day and month: Assume January 1st.  
However, if the partial date and the date of first infusion lie within the same year and the date of first infusion is not after the stop date of the medication, set to the date of first infusion. Otherwise, if date of first infusion is after the stop date for the medication, set to stop date of the medication.
- Missing day, month and year: Assume date of first infusion, if not after the stop date for the medication. Otherwise set to the stop date for the medication.

For the missing day imputation, the following examples should be used for reference:

- Example 1:  
Medication start: JUN2016  
Medication end: 20OCT2016  
Date of first infusion: 16OCT2016  
Medication start imputed: 01JUN2016
- Example 2:  
Medication start: OCT2016  
Medication end: 20OCT2016  
Date of first infusion: 16OCT2016  
Medication start imputed: 16OCT2016

- Example 3:  
Medication start: OCT2016  
Medication end: 20OCT2016  
Date of first infusion: 24OCT2016  
Medication start imputed: 20OCT2016

Partial end dates will be imputed as follows:

- Missing day: Assume the last day of the month.
- Missing day and month: Assume December 31st.
- Missing day, month and year: Assume that the medication is continuing.

In the case of the death of a patient, and the imputed end date is after the date of death, the end date will be imputed as the date of death.

A prior medication is defined as any medication where the start and stop dates or imputed start and stop dates are before the date of first infusion. A concomitant medication is defined as any medication that has an actual or imputed stop date on or after the date of first infusion or missing. The actual or imputed start date of a concomitant medication can be before or after the date of first infusion.

Prior and concomitant medications will be tabulated separately by treatment group and part, drug class (using ATC level 2), and preferred term (PT) for the safety population and safety population – Extension Study Period subset. The total number of prior and concomitant medications and the number and percentage of patients with at least one prior or concomitant medication will be summarized. The numbers and percentages of all prior and concomitant medications will also be summarized.

Additionally, prior and concomitant medications will be listed separately by treatment group for the safety population.

#### **9.1.1. Co-administration of Methotrexate and Folic Acid**

Data on co-administration of methotrexate and folic acid will be collected separately from all other medications. The same rules for date imputation and definitions of prior and concomitant will apply. The number of patients who started methotrexate or folic acid prior to first infusion of study drug and continued on or after the first infusion date will be summarized separately for methotrexate and folic acid. Additionally, the methotrexate dose at first infusion during each treatment course (mg/week) will be summarized. Summaries will be based on the safety population and safety population – Extension Study Period subset and presented by treatment group and part.

A listing will be provided by treatment group showing the details of co-administration of methotrexate and folic acid for each patient in the safety population.

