4.1.1 Inclusion Criteria

Each patient must meet all of the following criteria to be enrolled in this study:

- 1. Patient is male or female between 18 and 75 years old, inclusive.
- 2. Patient has a diagnosis of RA according to the revised 1987 ACR classification criteria (Arnett et al 1988) for at least 6 months prior to randomization.
- Patient has active disease as defined by the presence of 6 or more swollen joints (of 66 assessed) and 6 or more tender joints (of 68 assessed), and serum CRP ≥1.5 mg/dL (≥15 mg/L) or an ESR ≥28 mm/hour.
- 4. Patient has experienced an inadequate response to previous or current treatment with the anti-TNF agents infliximab (≥3 mg/kg; at least 3 infusions for at least 3 months), golimumab (50 mg once a month for at least 12 to 14 weeks or 2 mg/kg IV infusion for at least 3 months), adalimumab (40 mg every other week for at least 3 months), or etanercept (25 mg twice weekly or 50 mg once weekly for at least 3 months), or was intolerant to at least 1 administration of these agents. Patients who discontinued etanercept for at least 4 weeks, infliximab or adalimumab for at least 8 weeks, or golimumab for at least 10 weeks prior to randomization are permitted to enter the study.
Patients who received any other anti-TNF agents not in this list can be enrolled if the patient discontinued the treatment at least 4 weeks or 5 half-lives prior to randomization, whichever is longer.

5. Patient has a proper discontinuation period after treatment with interleukin-1 receptor (IL-1R) antagonist, interleukin-6 receptor (IL-6R) antibody, or abatacept. Patients who discontinued IL-1R antagonist for at least 4 weeks, abatacept for at least 8 weeks, or IL-6R antibody for at least 17 weeks prior to randomization are permitted to enter the study.

Patients who had any other biological drugs not in this list can be enrolled if the patient discontinued the treatment at least 4 weeks or 5 half-lives prior to randomization, whichever is longer.

- 6. Patient has received MTX treatment (7.5 to 25 mg/week orally or parenterally) for at least the past 12 weeks, with the last 4 weeks at a stable dose before Screening.
- 7. Patient has the following hematology laboratory test results at Screening:
 - Hemoglobin $\geq 8.0 \text{ g/dL}$
 - White blood cell count $\ge 3.5 \times 10^3$ cells/µL (SI [Système International d'Unités] units: $\ge 3.5 \times 10^9$ cells/L)

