#### **9.1.2. Prior Tumor Necrosis Factor (TNF) Antagonist History**

Data on prior use of anti-TNF agents administered to patients will be collected separately in the “Prior TNF Antagonist History” eCRF. The same rules for date imputation and definitions of prior and concomitant will apply. A table will be produced showing total number of prior TNF antagonists used and the number and percentage of patients with at least one prior TNF antagonist use who had prior use of TNF antagonists. Summaries will be based on the safety

population and safety population – Extension Study Period subset and presented by treatment group and part.

A listing of prior TNF antagonist history will be presented by treatment group for the safety population. The antagonist name, drug class, and PT, single dose, unit, frequency, route, start date, stop date and reason for discontinuation will be included for each patient.

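### General date-imputation rules, applied unchanged to methotrexate and prior anti-TNF records, can undercount both in their descriptive tables

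*SAP*

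**What the plan says.** SAP 9.1 completes partial medication dates so that each record can be placed in the prior or the concomitant table.

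- **Starts.** For a wholly unknown start: "Missing day, month and year: Assume date of first infusion, if not after the stop date for the medication". A year-only start also goes to the first infusion "if the partial date and the date of first infusion lie within the same year" and the stop is not earlier. A start known only to the infusion month is handled the same way.
- **Stops.** "Missing day: Assume the last day of the month". A year-only stop becomes 31 December. For a wholly unknown stop: "Missing day, month and year: Assume that the medication is continuing". Apart from the patient's death, nothing limits an imputed stop; in particular, first infusion does not.
- **Classes.** A drug is prior only if start and stop both fall before first infusion. It is concomitant if the stop is on or after first infusion, or missing.

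SAP 9.1.1 (methotrexate and folic acid) and SAP 9.1.2 (prior TNF antagonists) each contain the sentence "The same rules for date imputation and definitions of prior and concomitant will apply". Section 9.1.1 then counts patients who began methotrexate or folic acid before first infusion and carried on. For section 9.1.2, "A table will be produced showing total number of prior TNF antagonists used", together with the number of patients who had at least one.

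Protocol 4.1.1 requires methotrexate "for at least the past 12 weeks, with the last 4 weeks at a stable dose before Screening" (criterion 6). Criterion 4 requires at least 4 weeks off etanercept, 8 off infliximab or adalimumab, 10 off golimumab, and no less than 4 off any other anti-TNF agent before randomization. Randomization is on Day 0, before dosing.

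**The concern.** For ordinary co-medication it is a common cautious convention to lean towards on-study use when a date is incomplete. For these two record types the protocol has already settled the direction. In an eligible patient, methotrexate began before first infusion and anti-TNF treatment ended before it. The carried-over rules resolve the missing part of the date the opposite way.

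At stake is the description, by arm, of methotrexate background and previous anti-TNF treatment. Counts that fall short of what the entry criteria require would raise avoidable queries. Incomplete dates are foreseeable, because Protocol 5.7 asks for lifetime history of biologic and anti-TNF treatment.

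**Working it through.** **1. The SAP's own examples.** Applying the 9.1 start rules literally, with the stop imputed first:

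| Start recorded | Stop | First infusion | Imputed start | SAP states |
|---|---|---|---|---|
| JUN2016 | 20OCT2016 | 16OCT2016 | 01JUN2016 | 01JUN2016 |
| OCT2016 | 20OCT2016 | 16OCT2016 | 16OCT2016 | 16OCT2016 |
| OCT2016 | 20OCT2016 | 24OCT2016 | 20OCT2016 | 20OCT2016 |

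All three agree, so the reading of the rules is the SAP's own.

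**2. The same rules on the two record types**, first infusion 16OCT2016:

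| Record | Imputed date | Result |
|---|---|---|
| Methotrexate ongoing, start unknown | start 16OCT2016 | not counted as started before |
| Methotrexate ongoing, start 2016 | start 16OCT2016 | not counted as started before |
| Methotrexate ongoing, start JUN2016 | start 01JUN2016 | counted, correct |
| Methotrexate ongoing, start 2015 | start 01JAN2015 | counted, correct |
| Anti-TNF stop unknown | continuing | concomitant |
| Anti-TNF stop 2016 | stop 31DEC2016 | concomitant |
| Anti-TNF stop AUG2016 | stop 31AUG2016 | prior, correct |
| Anti-TNF stop 2015 | stop 31DEC2015 | prior, correct |

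The stop of 31DEC2016 lies 15 + 30 + 31 = 76 days after first infusion.

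**3. How often a partial date is misclassified.** Assume first infusion is equally likely on any day of a 365-day year, and let L be the true number of days from the methotrexate start, or the anti-TNF stop, to first infusion. A year-only date goes wrong when its year is the infusion year, which happens on 365 − L of the 365 days. The shortest permitted L for methotrexate is 12 × 7 + 1 = 85 days (Screening on Day −1). For anti-TNF it is 28, 56 or 70 days.

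| Record, year only | L (days) | Wrong |
|---|---|---|
| Methotrexate start | 85 | 280/365 = 77% |
| Methotrexate start | 180 | 185/365 = 51% |
| Methotrexate start | 365 | 0% |
| Anti-TNF stop | 28 | 337/365 = 92% |
| Anti-TNF stop | 56 | 309/365 = 85% |
| Anti-TNF stop | 70 | 295/365 = 81% |
| Anti-TNF stop | 180 | 185/365 = 51% |
| Anti-TNF stop | 365 | 0% |

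With the month known, an anti-TNF stop 28 days earlier is wrong only when it shares the infusion month: 3 days in each of seven 31-day months plus 2 in each of four 30-day months, 21 + 8 = 29 of 365 (8%). At 56 days or more it is never wrong. A methotrexate start known only to the infusion month also moves to the infusion day, but with L of at least 85 days this cannot arise in an eligible patient. A wholly unknown methotrexate start or anti-TNF stop is always misclassified.

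**4. Overall undercount.** The share of records lost is (share wholly unknown) + (share year-only) × (percentage above), plus the rare month-only anti-TNF term. The documents give none of these shares, so the total cannot be computed.

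**The case against.** The case for leaving the rules alone is that little depends on them.

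- Sites need approximate dates to verify a 12-week run-in and a 4- to 10-week washout, so a date known only to the infusion year may be uncommon. That stands: the frequency is unknown.
- The table wording in 9.1.2 is unclear. If every record on the Prior TNF Antagonist History page is counted whatever its dates, that table is spared. This is possible, but the section says the prior and concomitant definitions apply.
- Eligibility is documented elsewhere, in the inclusion/exclusion listings (SAP 7.6) and the deviation review (SAP 5.6). The imputation rules do not depend on arm, so no systematic imbalance is shown. Both points stand.

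A reader might infer more than the documents support:

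- **A table would show anti-TNF use on study.** SAP 9.1.2 plans no concomitant anti-TNF table. Records drop out of the prior table; they do not appear in another.
- **Methotrexate background would appear to be absent.** The dose at first infusion is summarised separately, and the listing remains.
- **Duration and number of prior TNF antagonists in SAP 7.2 are distorted.** SAP 9.1 confines its imputation to the prior and concomitant tables, and 7.2 does not say that it uses imputed dates.
- **SAP 7.5 has the same fault.** It is a separate rule for the diagnosis date. It takes the latest possible date and is already bounded: "If the imputed date is later than randomization date, then it will be imputed using the randomized date". It gives a conservative disease duration.

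**Conclusion.** The point holds as a minor one. Read literally, SAP 9.1.1 and 9.1.2 misclassify certain incomplete methotrexate and anti-TNF records, in a direction that inclusion criteria 4 and 6 rule out for eligible patients. The result is an undercount in two descriptive tables.

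The affected records are those with a wholly unknown date, those known only to the infusion year and, rarely, an anti-TNF stop known only to the infusion month. Dates from earlier years and nearly all dates with a known month are classified correctly. The percentages above are conditional on a partial date and on evenly spread infusion dates. The undercount itself may be small. The anti-TNF part also assumes that the stated definitions are applied to that table.

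The primary PK model (SAP 10.3) and the DAS28 model (SAP 11.2) do not use these dates. Folic acid is outside the point: the protocol sets no minimum pre-study duration for it, so a start on the infusion day is not necessarily wrong.

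**What to change.** Add to SAP 9.1.1 (methotrexate only) and SAP 9.1.2:

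- Cap an imputed methotrexate start and an imputed anti-TNF stop at the day before first infusion, with start no later than stop. Apply the cap only where the recorded part of the date allows it and the record does not show otherwise.
- Count every agent on the Prior TNF Antagonist History page as prior use, unless a recorded date shows use on or after first infusion.
- Flag imputed dates in the listings.

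With first infusion on 16OCT2016, the four misclassified dates in step 2 all become 15OCT2016 and are counted correctly. The other four do not change.

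Do not impute dates so that they meet the 12-week, washout or 6-month criteria. That would be circular and could hide real deviations. A methotrexate start recorded as 2015 with first infusion in mid-February 2015 cannot satisfy the 12-week criterion, and moving it into 2014 would contradict the recorded year. Leave such cases to the deviation review in SAP 5.6. Leave the folic acid rule and SAP 7.5 as they are.

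The cost is a few lines of SAP text and programming before database lock, with no new data.
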